### **6.4 Prior and concomitant medications**

Medications will be considered as prior if the start date of the medication is before the date of first dose of LCM. Medications will be considered as concomitant if it was taken at least once during treatment with LCM (ie, from the date of first administration of LCM through the date of last administration of LCM). Medications starting prior to first dose of LCM and continuing during treatment with LCM will be considered both, prior and concomitant medication.

For cases of partial or missing dates the rules described in Section 4.2.3 will be applied.

The number and percentage of subjects taking concomitant AEDs will be summarized by WHO-DD chemical subgroup (Level 4) and preferred drug name for the SS.

The number and percentage of subjects taking prior and concomitant medications (excluding AEDs) will be summarized separately by WHO-DD anatomical main group (Level 1) and therapeutic subgroup (Level 2) for the SS.

Vagus nerve stimulation will only be listed.

## **7 MEASUREMENTS OF TREATMENT COMPLIANCE**

### **7.1 Derivation of compliance**

Actual weight of LCM oral solution will be calculated at each visit using the following formula:

Actual weight of used oral solution (g) = Total weight of bottles (including caps) at Dispensation - Total weight of bottles (including caps) at Return

The actual weight used will also be determined for the Titration Period, Maintenance Period, and the entire Treatment Period by summing up the respective single actual weights.

The following formula will be used to calculate the expected weight of oral solution for the respective LCM dose:

Expected weight of used oral solution (g) = Daily prescribed oral solution (mL) x Number of days between visits x 1.1g/mL. (The estimated weight of 1mL of LCM is 1.1g.)

The expected weight will also be determined for the Titration Period, Maintenance Period, and the entire Treatment Period by summing up the respective single expected weights.

A subject's dosing compliance should be within 75-125% during each visit. Compliance to LCM dosing will be calculated for each visit, and will also be determined for the Titration Period, Maintenance Period, and the entire Treatment Period.

For oral solution, compliance will be calculated using the following formula:

Compliance (%) = Actual weight of used oral solution (g) / Expected weight of used oral solution (g) x 100

For tablets, compliance will be calculated using the following formula:

Compliance (%) = (100 x [number of 100 mg tablets dispensed – number of 100 mg tablets returned] + 50 x [number of 50 mg tablets dispensed – number of 50 mg tablets returned]) / dose given on the Drug accountability form of the eCRF x number of days)) x 100

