7.2 Treatment(s) to be administered

Lacosamide will be administered orally bid (at approximately 12-hour intervals in the morning and in the evening). Administration of oral solution by feeding tube is permitted for subjects who are unable to swallow the oral solution. At the end of the Baseline Period and completion of Visit 2, subjects who meet the eligibility criteria will commence a 6-week Titration Period (LCM dosing flexibility allowed based on tolerability).

As described in Section 5.1, subjects will initiate treatment with LCM oral solution at 2mg/kg/day, or LCM tablets at 100mg/day based on body weight. The dose will be titrated to a level to optimize tolerability and seizure control, not to exceed 12mg/kg/day (oral solution) for subjects weighing <50kg, or 600mg/day (tablets/oral solution) in subjects weighing ≥50kg. Subjects will increase the LCM dose in a stepwise fashion on a weekly basis to optimize tolerability and seizure control (see Figure 5-1 and Figure 5-2). During the Titration Period only, back-titration is permitted.

The planned doses for each week of the Titration Period for subjects taking the LCM oral solution and tablet formulations are displayed in Table 7-1.

Table 7-1: Lacosamide dose titration during the Titration Period

Body weight category (formulation)	Flexible doses for the Titration Period by study week					
	Week 1	Week 2	Week 3	Week 4	Week 5	Week 6
<50kg (oral solution)	2mg/kg/day	4mg/kg/day	6mg/kg/day	8mg/kg/day	10mg/kg/day	12mg/kg/day
≥50kg (tablets/oral solution)	100mg/day	200mg/day	300mg/day	400mg/day	500mg/day	600mg/day

LCM=lacosamide

Note: Subjects weighing ≥50kg who are unable or unwilling to swallow tablets can be dispensed LCM oral solution instead.

After completion of Week 1, investigators will assess whether a subject would tolerate a further dose increase or whether a subject should hold the Week 1 dose for a longer duration. This hold will be at the investigator's discretion. The flexible LCM dosing over the remainder of the Titration Period is outlined in Table 7-2.

Table 7–2: Flexible LCM dosing during the Titration Period

Body weight category (formulation)	Target dose increase/week ^a (titration)	Dose decrease per back-titration step		Subsequent dose increase ^b (dose increase after back -titration step)	
		Min	Max	Min	Max
<50kg (oral solution)	2mg/kg/day	1mg/kg/day	2mg/kg/day	1mg/kg/day	2mg/kg/day
≥50kg (tablets/oral solution)	100mg/day	50mg/day	100mg/day	50mg/day	100mg/day

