7.7 Procedures for monitoring subject compliance

At each visit after IMP is dispensed, subjects must return all used, unused, and empty IMP containers. Drug accountability must be done in the subject's presence in order to obtain explanations regarding discrepancies in compliance with the dosing regimen. Drug accountability must be recorded on the Drug Accountability form.

If a subject is found to be persistently noncompliant (defined as <75% or >125% compliant with the dosage schedule), the sponsor, in conjunction with the investigator, will make a decision as to whether the subject should be withdrawn from the study.

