8.2.4 Visit 4 (Week 4)

Assessments for Visit 4 (end of Week 4 ± 2 days) are the same as those described for Visit 3 (end of Week 2) in Section 8.2.3. This visit is optional and will only be required if a subject requires further LCM dose adjustment.

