### 8.4 Extent of exposure

The duration of LCM exposure for each study period will be calculated as follows:

Duration of LCM (days) = date of last dose of LCM during the respective period minus the date of first dose of LCM during the respective period plus 1.

For the calculation of the mean daily dose during the Maintenance Period, the total dose for each entry in the LCM administration form with at least 1 day within the Maintenance Period will be calculated as follows:

Total dose = (Morning dose + evening dose) x (administration stop date - administration start date + 1)

If the administration start date is before the start date of the Maintenance Period the start date of the Maintenance Period will be used instead. If the administration stop date is after the end date of the Maintenance Period the end date of the Maintenance Period will be used instead.

The mean daily dose during the Maintenance Period will be calculated as the sum of the total doses for each entry in the study medication administration form with at least 1 day within the Maintenance Period divided by the duration of LCM exposure during the Maintenance Period. Days during an analysis period with unknown dosing will be excluded from both the numerator and the denominator for the calculation of the mean daily dose.

The mean daily dose will be presented in mg/kg/day. For patients who received tablets, the mean daily dose will be normalized by the baseline weight.

The duration of LCM exposure will be summarized with descriptive statistics overall (ie, for the entire Treatment Period) as well as separately for each study period (Titration Period, Maintenance Period).

In addition, the duration of LCM exposure will be summarized in 14-day categories up to the scheduled duration of the period:

- Treatment Period:  $\leq 14$  days,  $>14-\leq 28$  days,  $>28-\leq 42$  days,  $>42-\leq 56$  days,  $>56-\leq 70$  days,  $>70-\leq 84$  days,  $>84-\leq 98$  days,  $>98-\leq 112$  days,  $>112-\leq 126$  days,  $>126-\leq 140$  days,  $>140-\leq 154$  days,  $>154-\leq 168$  days, and  $>168$  days.
- Titration Period:  $\leq 14$  days,  $>14-\leq 28$  days,  $>28-\leq 42$  days, and  $>42$  days.
- Maintenance Period:  $\leq 14$  days,  $>14-\leq 28$  days,  $>28-\leq 42$  days,  $>42-\leq 56$  days,  $>56-\leq 70$  days,  $>70-\leq 84$  days, and  $>84$  days.

The mean daily dose during the Maintenance Period will be summarized descriptively.

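### SAP 7.1 applies one daily dose to all days between visits although the dose changes inside titration intervals, so some fully adherent subjects, mainly early drop-outs, fall in the wrong compliance category

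*SAP*

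**What the plan says.** For oral solution, SAP 7.1 introduces its denominator with "The following formula will be used to calculate the expected weight of oral solution for the respective LCM dose" and defines it as "Expected weight of used oral solution (g) = Daily prescribed oral solution (mL) x Number of days between visits x 1.1g/mL". For tablets the denominator is "dose given on the Drug accountability form of the eCRF x number of days". Neither formula says what to do when two doses apply within one interval. Period totals of these weights follow by addition: "The expected weight will also be determined for the Titration Period, Maintenance Period, and the entire Treatment Period by summing up the respective single expected". SAP 7.1 expects 75-125% at each visit. SAP 7.2 tabulates and categorizes (<75%, 75-125% inclusive, >125%) only the Titration, Maintenance and Treatment Periods.

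Protocol 7.2 states: "Subjects will increase the LCM dose in a stepwise fashion on a weekly basis". Table 7-1 gives 2, 4, 6, 8, 10 and 12 mg/kg/day for Weeks 1 to 6 below 50 kg, and 100 to 600 mg/day in 100 mg steps from 50 kg. Back-titration steps are unlimited. Clinic visits with drug return fall at Weeks 2, 4, 5 and 6. For Visit 4, Protocol 8.2.4 says: "This visit is optional and will only be required if a subject requires further LCM dose adjustment", and Protocol 8.2.5 says the same of Visit 5. The Week 1 and Week 3 contacts are by telephone, with no drug return (Protocol 8.1.2 and 8.2.2).

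**The concern.** A compliance ratio should equal 100% when the child takes exactly what was prescribed. Here the numerator (drug used) follows the real dose path, while the denominator freezes the dose at one level for the interval. On the planned schedule the steps at the ends of Weeks 1 and 3 fall between clinic visits, so the ratio departs from 100% with no departure from treatment. The text also leaves open which dose is frozen, and for Visit 2-3 that choice changes the answer by a factor of two.

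At stake is the meaning of the Titration and Treatment Period compliance tables. The Titration Period ends at Early Termination if that comes before Visit 6 (SAP 3.2.3), so for an early drop-out the distorted first interval is the whole tabulated Titration value and no later interval dilutes it. In a safety and tolerability study these are the subjects whose compliance a reader will look at most closely.

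**Working it through.** The documents state no compliance result, so there is no figure of theirs to reproduce. The check takes a subject with perfect adherence and applies SAP 7.1 literally.

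**Inputs.** Weekly doses from Table 7-1. Nominal intervals: Visit 2-3, 14 days; Visit 3-4, 14 days; Visit 4-5, 7 days; Visit 5-6, 7 days. Maintenance is 84 days at the final dose (the protocol keeps it stable). Body weight, the 10 mg/mL strength (Protocol 7.1) and 1.1 g/mL cancel in the ratio, so everything can be done in mg/kg. The tablet steps give the same percentages, e.g. Visit 2-3: 2100/1400 = 150%.

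**Formula.** Compliance = 100 × (sum of daily doses taken) / (single dose × days between visits). The single dose is set first to the start-of-interval dose and then to the end-of-interval dose, because the SAP does not choose.

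**By interval, full schedule**

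| Interval | Taken (mg/kg) | Expected, start dose | Score | Expected, end dose | Score |
|---|---|---|---|---|---|
| Visit 2-3 | 7×2 + 7×4 = 42 | 14×2 = 28 | 150.0% | 14×4 = 56 | 75.0% |
| Visit 3-4 | 7×6 + 7×8 = 98 | 14×6 = 84 | 116.7% | 14×8 = 112 | 87.5% |
| Visit 4-5 | 7×10 = 70 | 70 | 100% | 70 | 100% |
| Visit 5-6 | 7×12 = 84 | 84 | 100% | 84 | 100% |

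The ±2-day window at Visit 3 widens the first row. With the step after day 7, a visit at day 12 gives 34/24 = 141.7% or 34/48 = 70.8%; a visit at day 16 gives 50/32 = 156.3% or 50/64 = 78.1%.

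**By tabulated period**

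| Path, perfect adherence | Period | Start dose | End dose |
|---|---|---|---|
| Full schedule, all visits held | Titration | 294/266 = 110.5% | 294/322 = 91.3% |
| Same | Treatment | 1302/1274 = 102.2% | 1302/1330 = 97.9% |
| 2, 4, 6, 8, 8, 8 mg/kg/day, Visits 4 and 5 not held | Titration | 252/196 = 128.6% | 252/280 = 90.0% |
| Same | Treatment | 924/868 = 106.5% | 924/952 = 97.1% |
| Stops at day 10 | Titration | 26/20 = 130% | 26/40 = 65% |
| Any path, stable dose | Maintenance | 100% | 100% |

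The day-10 subject has taken 7×2 + 3×4 = 26 mg/kg. The start dose puts this subject above 125% and the end dose puts the same subject below 75%. Neither choice of a single dose rescues the formula.

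**After the correction.** Summing dose × days at that dose makes the denominator equal to the amount taken, so every interval and period above scores 100.0%.

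**The case against.** The strongest defence is that SAP 7.1 ties expected weight to the respective dose and adds up single expected weights, and that the accountability form, which the documents do not include, might carry one line per dose level. If it did, much of the problem would disappear. That point stands as a limit on certainty, but the multiplier written for solution is days between visits, not days at a dose. If a per-dose calculation is intended, the text needs to say so.

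Three stronger readings are tempting and are not supported:

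- *Every adherent child scores up to 150% and is flagged noncompliant.* The 150% applies to one interval under one choice of dose; the other choice gives 75.0%, inside the inclusive range. Nor is 150% a maximum, given the visit window. Per-visit values are calculated but not categorized, and the full-schedule Titration and Treatment values stay in range on either reading.
- *Adherent children would be withdrawn.* Protocol 7.7 concerns subjects "persistently noncompliant (defined as <75% or >125% compliant with the dosage schedule"), and leaves withdrawal to a joint decision of sponsor and investigator. Nothing says that sites use the SAP formula.
- *SAP 8.4 already solves this.* Its dated-entry rule, "Total dose = (Morning dose + evening dose) x (administration stop date - administration start date + 1"), is specified only for mean daily dose in the Maintenance Period, when the dose is stable. Its entries may also record doses taken, which would make a compliance denominator built on them partly circular.

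It is also fair to say that compliance defines no analysis set and enters no primary, secondary or efficacy variable.

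**Conclusion.** The point holds in limited form. As written, the SAP 7.1 rule gives wrong expected use whenever the dose changes inside a visit interval, and scheduled titration makes that happen in Visit 2-3 and Visit 3-4. For a fully adherent subject the tabulated Titration value ranges from about 90% to 129% in the 6-week paths shown, and is 130% or 65% for a subject who stops at day 10. Some adherent subjects, mainly early drop-outs, therefore land in a wrong SAP 7.2 category, in a direction that depends on an unstated choice. The full schedule stays in range, Maintenance is unaffected, and the consequence is confined to descriptive compliance summaries. It is worth correcting but does not threaten the study's main results.

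The figures assume perfect adherence, nominal visit timing except where the window is shown, dose steps exactly at week ends, and one dose per interval in the denominator. Which dose the accountability form records cannot be seen, so both readings are given.

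**What to change.** In SAP 7.1, define expected use for each interval as the sum, over dated dose entries, of prescribed daily dose × days at that dose, truncated at visit and period boundaries. Apply the same sum to solution (converted with 10 mg/mL and 1.1 g/mL) and to tablets, then add the intervals to obtain the Titration, Maintenance and Treatment Periods. This extends to compliance the dated-entry approach that SAP 8.4 uses for Maintenance mean daily dose. First confirm that the entries hold the prescribed dose and not the dose taken; if they do not, name the source of the prescribed dose and its dates. The unbalanced parentheses in the tablet formula can be corrected in the same edit.

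The cost is a short change of wording and minor extra programming. No dose, visit or clinical rule changes.

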### **7.2 Presentation of compliance**

Compliance will be summarized separately for the Treatment Period, the Titration Period and the Maintenance Period. It will be presented with descriptive statistics and additionally categorized as <75%, ≥75% to ≤125%, and >125%

## **8 SAFETY ANALYSES**

All safety analyses will be conducted for the SS.

### **8.1 Primary safety variables**

#### **8.1.1 Generalized spike-wave discharges**

The actual values of generalized spike-wave discharges per interpretable hour on 24-hour ambulatory EEG as well as changes from Baseline will be summarized descriptively by visit.

Furthermore, a frequency table will be presented for the number of subjects with an increase of at least 30% and an increase of at least 50% at Visit 6 compared to Baseline.

### 8.1.2 Generalized seizures

Days with any generalized seizures per 28 days (GSD/28d) will be based on the seizure diary and will be derived separately for the Baseline Period, the Titration Period, and the Maintenance Period. Basis for the calculation will be the number of days with at least 1 generalized seizure (GSD) (absence, myoclonic, clonic, tonic, tonic clonic, atonic, partial evolving to secondarily generalized) during the considered study period and the number of days in the considered study period for which seizure information was provided (D):

$$\text{GSD/28d} = \text{GSD} \times (28/\text{D})$$

The days with any generalized seizures per 28 days will only be derived for subjects who completed or discontinued during the respective study period. For subjects who discontinued during the Titration Period, the missing value of the Maintenance Period will be imputed as described in Section 4.2.

Descriptive statistics will be provided for actual values and changes from Baseline for days with any generalized seizures per 28 days by study period. This summary will be repeated by syndrome subgroups (as described in Section 4.8).

## 8.2 Secondary safety variables

### 8.2.1 3Hz spike-wave discharges

The actual counts of 3Hz spike-wave discharges (during waking hours) on 24-hour ambulatory EEG as well as changes from Baseline will be summarized descriptively by visit.

Furthermore, a frequency table will be presented for the number of subjects with an increase of at least 30% and an increase of at least 50% at Visit 6 compared to Baseline.

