13.3.2 Secondary safety variables

The actual change in the count of 3Hz spike-wave discharges on 24-hour ambulatory EEG from Visit 2 to Visit 6 will be calculated and summarized descriptively.

Adverse events will be coded using the Medical Dictionary for Regulatory Activities (MedDRA®). Summary tables for number and percentage of subjects reporting at least 1 TEAE tabulated by System Organ Class and preferred term will be presented. Furthermore, TEAEs that lead to early discontinuation from the study and serious TEAEs will be tabulated. Treatment-emergent AEs will be defined as those events which start on or after the date of first LCM administration and within 30 days following the date of last LCM administration, or whose severity worsens within this time frame.

Subject withdrawal due to AEs will be analyzed by presenting number and percentage of subjects with "AE(s)" given as primary reason of premature study discontinuation.

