##### 2.2.1.2 Secondary safety variables

The secondary variables assessing safety are:

- Changes in count of 3Hz spike-wave discharges (during waking hours) on 24-hour ambulatory EEG from Visit 2 to Visit 6

- Adverse events (AEs) as reported spontaneously by the subject and/or caregiver, or observed by the investigator
- Subject withdrawals due to AEs

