### 8.3 Exploratory safety variables

A frequency table will be presented for the number of subjects with a decrease of at least 30% and a decrease of at least 50% in generalized spike-wave discharges on 24-hour EEG at Visit 6 compared to Baseline by syndrome subgroups

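### The SAP's 3Hz discharge worsening table uses raw waking-hour counts, so it reflects differences in readable waking time between the two EEGs as well as any change in discharge rate

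*SAP*

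**What the plan says.** Both EEG variables come from the same ambulatory recordings at Visits 2, 6 and 9 (or early termination).

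- **Generalized discharges (SAP 8.1.1, primary).** The summary covers "The actual values of generalized spike-wave discharges per interpretable hour on 24-hour ambulatory EEG as well as changes from Baseline", so usable recording time is divided out.
- **3Hz discharges (SAP 8.2.1, secondary).** "The actual counts of 3Hz spike-wave discharges (during waking hours) on 24-hour ambulatory EEG as well as changes from Baseline will be summarized descriptively". There is no divisor.
- **Cut-offs.** Both sections then tabulate subjects with "an increase of at least 30% and an increase of at least 50% at Visit 6 compared to Baseline".
- **Protocol.** Section 13.3.2 plans "The actual change in the count of 3Hz spike-wave discharges on 24-hour ambulatory EEG from Visit 2 to Visit 6". Section 13.3.1 likewise plans a change in count for generalized discharges. SAP 2.2.1.1 and 2.2.1.2 list both variables as counts.
- **Decreases (SAP 8.3).** The exploratory table covers 30% decreases and a "decrease of at least 50% in generalized spike-wave discharges on 24-hour EEG at Visit 6 compared to Baseline by syndrome subgroups", without naming the unit.
- **Changes from protocol (SAP 3.9).** None is declared.

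Neither document sets a minimum readable or waking recording time. Protocol 8.2.1, 8.2.6 and 8.3.4 ask the subject to return about 24 hours after the electrodes are attached.

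**The concern.** By dividing by interpretable hours in 8.1.1, the SAP accepts that usable time can differ between a child's recordings. SAP 8.1.2 does the same for seizure days, which are scaled by the days with diary information. The 3Hz variable is the one left unscaled, although two things limit its window: the trace must be readable and the child must be awake.

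A percentage cut-off on an unscaled count can fail in two ways. A child whose rate has not changed can be counted as worse because more readable waking time was captured at Visit 6. A child whose rate has risen can be missed because less was captured. With no control arm, nothing shows how much of the table such measurement variation would produce on its own. About 50 subjects are planned, so each misclassified child moves a whole-group percentage by about 2 points (1/50).

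SAP 8.2.1 summarises by visit and SAP 9.1 describes no separate EEG analysis. The raw count therefore appears also to serve the Visit 9 or early termination change that SAP 2.2.2.1 lists under preliminary efficacy.

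**Working it through.** The plan gives no figure to reproduce: there is no sample size calculation, and no expected discharge rate or recording time.

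**Identity.** Let r be the discharge rate per interpretable waking hour and H the interpretable waking hours. Then count = r × H, and

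count ratio (Visit 6 / Visit 2) = rate ratio × hours ratio.

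**Inputs from the documents.** The cut-offs are ratios of 1.3 and 1.5 (SAP 8.2.1). All hours below are assumptions chosen for illustration.

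**Rate unchanged (rate ratio 1)**
- 10 h to 13 h: 13/10 = 1.30, so +30% and flagged at the lower cut-off.
- 8 h to 12 h: 12/8 = 1.50, so +50% and flagged at both.
- 12 h to 14 h: 14/12 = 1.167, so +16.7% and not flagged.

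**Rate truly higher**
- Rate +50%, 14 h to 10 h: 1.5 × 10/14 = 1.071, so +7.1% and missed at both cut-offs.
- Rate +30%, 13 h to 12 h: 1.3 × 12/13 = 1.20, so +20.0% and missed.
- A true +50% falls below the 30% cut-off once the hours ratio is under 1.3/1.5 = 0.867.

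**Rate rise needed to be flagged if hours fall by 20% (hours ratio 0.8)**
- 30% cut-off: 1.3/0.8 − 1 = 62.5%.
- 50% cut-off: 1.5/0.8 − 1 = 87.5%.

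**Equal hours.** The hours ratio is 1, so count and rate give the same percentage change.

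**How often this could matter.** A simulation of 400,000 subject pairs assumed Poisson counts at 20 discharges per hour, and log-normal waking hours with mean 12, drawn independently at each visit. Only the coefficient of variation (CV) of the hours was varied.

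| CV of hours | No true change, flagged ≥30%: count / rate | No true change, flagged ≥50%: count / rate | True +50%, flagged ≥30%: count / rate |
|---|---|---|---|
| 0% | 0.2% / 0.2% | 0.0% / 0.0% | 95.9% / 95.9% |
| 10% | 6.0% / 0.2% | 0.8% / 0.0% | 81.0% / 95.7% |
| 15% | 12.8% / 0.2% | 4.0% / 0.0% | 73.7% / 95.6% |
| 20% | 18.8% / 0.3% | 8.5% / 0.0% | 68.8% / 95.5% |
| 30% | 26.9% / 0.4% | 17.1% / 0.0% | 63.2% / 95.2% |

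The simulation gives the direction and a range. It does not estimate what this trial would show, because the true variation in hours is unknown.

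**The case against.** **The count is what was pre-specified.** The protocol and SAP 2.2.1.2 both define the 3Hz variable as a count, so 8.2.1 is faithful and 8.1.1 is the section that departs. This is correct. It supports keeping the count as a summary and declaring the departure in 3.9. It does not justify two different units under the same percentage cut-offs.

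**Total waking discharges may be a legitimate target.** If a child is awake longer and has more discharges, the total burden is higher, so count against rate is partly a choice of estimand. This stands for time awake. It does not stand for unreadable recording, where the discharges occurred but were not counted.

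**The recording is standardised at about 24 hours.** This limits variation in total length. It fixes neither waking nor readable time, and nothing in the documents shows how much either varies.

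**A distorted 3Hz table would not by itself hide clinical worsening.** Absence-seizure days are analysed with a diary-day denominator (SAP 8.1.2, 9.1.1). Clinically significant seizure worsening is recorded as an adverse event (protocol 11.1.1), and adverse events are tabulated overall and by syndrome (SAP 8.2.2). This stands and lowers the severity.

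**Stronger readings that the documents do not support**
- A reader might infer that the table tracks recording time and not discharge rate. It tracks both.
- A reader might treat the 3Hz variable as the EEG marker of the absence-seizure increase, about 10% of subjects, reported from SP0961 (protocol section 2). The protocol reports that increase as adverse events, mentions no EEG finding, and says drug effect could not be separated from the natural course of the disease.
- A reader might infer that SAP 8.3 deliberately uses a different unit. It may only be naming the variable in short form, as SAP 2.2.1.4 does, so the need is for clarification.

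**Conclusion.** The inconsistency is real and nothing elsewhere in the documents resolves it. As written, the 3Hz increase table can classify a child as worse, or fail to, because interpretable waking time differed between Visit 2 and Visit 6.

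The arithmetic is exact, but the size in this trial is unknown because it depends on variation in waking hours that the documents do not give. Under the simulation's assumptions, the share of unchanged children flagged at the 30% cut-off runs from 0.2% with no variation in hours to 26.9% at a CV of 30%.

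This should be fixed, but it is not a blocking fault. The variable is secondary, all analyses are descriptive, no decision rule is tied to the table, and no error rate or power is affected.

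**What to change.** 1. **SAP 8.2.1.** Base the 3Hz values, changes from Baseline and both increase cut-offs on discharges per interpretable waking hour. Keep the protocol-defined count as a supporting summary, and list the interpretable waking hours for each EEG.
2. **Before finalising this,** confirm with the EEG reader that interpretable waking time is recorded. The documents do not describe the reading output, so having interpretable hours for 8.1.1 does not show that waking interpretable hours are stored.
3. **SAP 8.3.** State that the decrease table uses the same unit per interpretable hour as 8.1.1.
4. **SAP 3.9.** Replace the entry of no changes with the count-to-rate changes from the protocol, including the one already made for generalized discharges.

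The cost is SAP wording and some programming if the hours are available. If they are not, the reader would have to supply them. The change is best made before results are seen, so that the unit for a safety variable is not chosen after the fact.
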